3.1 Assessment and management of risk

Name of	Potential risk	Risk Frequency	Risk Management
treatment	voice alteration	≥3%	DMC configured to mitigate participant
Recombinant	pharyngitis		safety and data integrity risks
human DNase 1 (dornase	rash		
alfa)	laryngitis		
administered	chest pain		
by nebulisation	conjunctivitis		
	-		
Recombinant human DNase	rhinitis	less than 3%	DMC configured to mitigate participant
1 (dornase	decrease in FVC of		safety and data integrity risks
alfa)	≥10%*		
administered	fever		
by nebulisation	dyspnoea		
Recombinant human DNase	There is a low potential immunogenicity risk	Low (2-4%)	There have been no reports of anaphylaxis attributed to the
1 (dornase	and antibodies to		administration of dornase alfa. Urticaria,
alfa)	dornase alfa will not be		mild to moderate, and mild skin rash
administered	measured in this study		have been observed and have been
by nebulisation			transient. Within all of the studies, a small percentage (average of 2-4%) of
TEDUISACION			people treated with dornase alfa
			developed serum antibodies to dornase
			alfa. None of these people developed
			anaphylaxis, and the clinical significance of serum antibodies to dornase alfa is
			of serum antibodies to dornase alfa is unknown.

The table below summarises the risks, frequencies and mitigations of COVASE trial

Failure to recruit patients	unlikely	Feasibility data suggests that sufficient participants can be recruited over the time specified. However, additional sites are available through the NOCRI respiratory TRP that represents 10 of the UK BRCs
Delay in dornase alfa supply	unlikely	UCLH pharmacy to check and put a PO as soon as the grant is awarded and REC/MHRA approval received.
Delay in eRapid supply in the UK	unlikely	UCLH pharmacy to check and put a PO as soon as the grant is awarded and MHRA/REC approval received.
Competing clinical trials	unlikely	There are trials currently ongoing at UCLH that will compete. Trials at UCLH are prioritised and overseen by the COVID-19 committee to ensure equitable recruitment of hospitalised participants to all ongoing trials. Deliverability of trials is also under their management.
Staff sickness due to COVID-19	unlikely	Additional nursing support is available to cover levels of 25-50% due to COVID-19 infection and time off work.

*Single measurement only, does not reflect overall FVC changes.

The table below summarise the risks and mitigations of all test above standard care that are being performed in the COVASE Trial:

Intervention	ntervention Potential risk Risk Management	
Nebulisation of dornase alfa to participants with COVID-19	As dornase alfa is approved for the treatment of children and adults with CF, we will be using the drug 'off-label' for the first time in participants with COVID- 19. There is a low risk that the safety and tolerability in this population may be different to that expected from CF	We will therefore use 'sentinel' dosing for the first three participants enrolled. This means that the three sentinel participants will each commence dosing and safely complete 2 days of treatment individually, before another participant is dosed. Thereafter (participant 4 and onwards) enrolment and dosing may occur in parallel.

venepuncture include	Experienced hospital staff will be drawing the blood and will minimise these potential risks
----------------------	----------------------------------------------------------------------------------------------------

In accordance with the MRC/DH/MHRA Joint Project Risk-adapted Approaches to the Management of Clinical Trials of Investigational Medicinal Products, this trial is categorised as:

Type B = Somewhat higher than the risk of standard medical care

4 Objectives and endpoints

Primary objective: to assess the effect of nebulised dornase alfa on the inflammatory/immune responses in hospitalised participants with COVID-19

- Primary endpoint:
 - Changes in acute phase reactant (C-Reactive Protein (CRP))

Secondary objective: to assess the effect of nebulised dornase alfa on clinical responses in hospitalised participants with COVID-19 compared to control group.

- Secondary endpoints:
 - Physical exam and vital signs
 - Whole blood count and differential count
 - Incidence of Mechanical Ventilation (MV)
 - Time on MV
 - ProCalcitonin (PCT)
 - D-dimer
 - Oxygen requirement (oxygen flow or oxygenation index)
 - Length of ICU stay [hours]
 - Length of stay in the hospital [days)
 - Incidence of multi-organ failure according to SOFA (Sepsis-related Organ Failure Assessment)
 - Incidence of Ventilator-Associated Pneumonia (VAP) or hospital acquired pneumonia
 - Acute physiology score + age points + chronic health points (APACHE score)
 - Ordinal score (WHO scoring tool)
 - Survival at Day35

Exploratory objective: to assess the effect of nebulised dornase alfa on inflammation, biomarkers of NETs, coagulation, complement activation and haemolysis in hospitalised participants with COVID-19

- Exploratory endpoints may be measured in the circulation (blood) and, when these are available, in bronchial secretions (spontaneous expectorant or routine bronchoscopy during MV). They may include, but are not limited to:
 - Circulating pro-inflammatory cytokines (e.g. IL-6, TNFα, IL-1β, IL-8)
 - Cell-free DNA (cfDNA)
 - Circulating histone
 - Citrullinated H3
 - NET Elisa assay
 - NET formation assay
 - Coagulation (e.g fibrin, tissue factor, Von Willebrand factor, thrombin, thromboxane A2)
 - Complement cascade (e.g C1q)
 - Haemolysis (e.g RBC lysis)
 - Expression profiling of white blood cells by RNA seq

5 Trial design

5.1 Overall design

A single-site, randomised, controlled, parallel design, open-label investigation of an approved nebulised recombinant human DNase enzyme (dornase alfa) to reduce hyperinflammation in hospitalised participants with COVID-19 (the COVASE Trial: Figure 2).

Figure 2: COVASE Trial Schematic

Participants will be screened, consented, enrolled and randomised up to 3 days after they are admitted to the hospital. They will be randomised in a 3:1 ratio to receive BAC + dornase alfa or

BAC alone. A total of 40 participants will be enrolled (30 to receive BAC plus dornase alfa and 10 to receive BAC). On Day1 to Day7 of the trial, participants randomised to the active arm, will receive 2.5mg BID nebulised dornase alfa in addition to BAC. On Day1, Day3, Day5 and Day7, blood samples will be drawn in both trial arms in order to test pharmacodynamic endpoints (PD), biomarkers and clin labs. Clinical assessments will be undertaken daily (as per UCLH clinical guidelines). Participants will be followed until discharge or death or a maximum of 28 days follow-up.

A sample size re-estimation is planned when 12 participants have been randomised. This analysis will ensure that the assumptions made in the sample size calculation remain valid. However, if the variability is higher than expected then up to an additional 10 participants will be enrolled and treated with dornase alfa (up to 50 participants in total).

CRP has been chosen as the Primary Endpoint because it is a clinically important marker of inflammation and is used to make clinical treatment decisions. In addition, it is induced by the over-exuberant inflammation mediated by the NETs and inflammatory histones. CRP is a prognostic marker and correlates with clinical symptoms and response to therapy. Thus, CRP is at the centre of the COVID-19 disease pathway: from NETS to CRP to clinical disease progression.

Based on clinical judgement, it may be decided to keep some participants on treatment for up to 14 days. In particular, if participants have significant benefits from therapy, but show relapses of the COVID-19 inflammatory state (rising CRP and increasing oxygen requirements in the absence of bacterial infection), on completing 7 days of treatment, then the medical team have the choice of reinstating dornase alfa treatment for up to 7 further days (14 days in total). Blood sampling, as specified, will continue until the last day of dosing with dornase alfa.

Study controls

Due to the evolving situation with hospitalised COVID-19 participants, the burden on the NHS and the availability of other COVID-19 trials, it is considered inappropriate to conduct a placebocontrolled study. Therefore, a randomised, controlled, open-label approach where dornase alfa is administered on top of BAC and compared to BAC alone has been adopted.

The data derived from the 10 participants who are randomised to the BAC arm of the study who do not receive dornase alfa will provide control data for all of the study endpoints.

The 30 participants randomized to BAC + dornase alfa will be compared to 10 randomised controls from the COVASE study. In addition, 10 participants in other clinical trials on BAC (biobanked samples) and 60 participants from a historic database of the first 120 people with COVID-19 treated at UCLH will also be used as comparator data.

However, to enhance the control group, a hybrid approach will be applied such that additional data will be combined with the randomised controls, illustrated in Figure 3. The sample size calculation indicates that 90 evaluable participants are required (60 control:30 active). These control data may include: data from the randomised BAC arm, historic COVID-19 UCLH database, biobanked samples from other ongoing trials and observational trials in COVID-19.

This hybrid strategy allows two things:

- provides comparators for all of the study objectives (including limited data for the exploratory objectives)
- demonstrates that the historic controls are representative/similar to the study population

Comparator data from UCLH is available as historic controls for the Primary and Secondary Endpoints. A database of the first 120 participants with COVID-19 admitted to UCLH is available and being analysed currently. CRP is routinely measured daily (or on alternate days) in all participants admitted to UCLH and will be used to control for the Primary Endpoint. All of the Secondary Endpoints are also routinely measured and will be available in the database. Participants in the database will be selected to act as controls as follows:

- 1. Apply the inclusion and exclusion criteria of the COVASE study
- 2. Additional selection to identify closest matches using a propensity score based on age, gender, BMI, baseline CRP, oxygen requirements and the number of comorbidities.

At least 60 control participants are expected to be available to act as controls.

Other ongoing and planned trials may be a source of cytokine data as well as biobanked samples that could be used to provide control information on the exploratory endpoints (e.g. ISARIC and RECOVER Trials) assuming suitable consent is available.

6 Off-label use of an Approved Medicinal Product (Pulmozyme)

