6.5 Concomitant medication

Participants in the COVASE trial will continue to receive best available care (BAC) per UCLH guidelines. Dornase alfa will be administered in addition to BAC.

BAC currently consists of symptomatic relief: antipyretics, analgesics and intravenous fluids if needed. In addition, patients may need supplemental oxygen and/or mechanical ventilation.

There is no basis to support a drug-drug interaction risk, as this is a recombinant human protein that is administered directly to the lungs. Systemic exposure is very low and dornase alfa is cleared by proteinases present in the lungs.

There is a potential risk that other medications administered as BAC may affect the endpoints in the study e.g. decrease CRP. However, this cannot be avoided and will be considered in the analysis plan for the data. Furthermore, a sample-size re-estimation is planned in order to take this potential source of unexpected variability into account.

Concomitant medications will be recorded in the participant's medical records/CRF.

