11.2 Sample size and recruitment

11.2.1 Sample size calculation

Sample size calculations were produced using the proc power function in SAS Version 9.4. These were conducted to achieve 80% power to detect difference in the active arm versus the control group at the 5% level of significance. Based on a mean of 99mg/L in the control group and a common standard deviation of 62mg/L derived from the literature (Han et al., 2020; Zhou, 2020), a total sample size of 90 participants would provide sufficient power to detect a greater than a 40% relative difference for CRP in the dornase alfa group compared to the control group. Given the reported average values in severe and non-severe participants and on clinical observations from COVID-19 patients, this difference would be achievable and clinically relevant.

This study will use existing data collected at UCLH from participants admitted with COVID-19 as a comparator group. Participants in the database will be selected to act as controls as follows:

- Apply the inclusion and exclusion criteria of the COVASE study
- Additional selection to identify closest matches

This will give the correct ratio of active versus comparator (ratio of 1:2). To achieve the required power, this would result in 30 participants in the active treatment group and at least 60 in the control. An additional 10 participants will be recruited as a control for the exploratory objectives and to compare the characteristics of enrolled participants with the historical controls. This gives a total of 40 participants enrolled in the study and 60 historical controls.

Participants who drop out of the study will be replaced so the sample size relates to the number of evaluable participants required.

A re-estimation of the sample size will be carried following an interim analysis when 12 participants have been randomised.

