#### **11.1 Primary endpoint analysis**

#### **Exploristics Limited**

### Identifier: EXP20012 Clinical Study Identifier: 132333

The primary endpoint will be compared between groups using a repeated measures mixed model, adjusted for age, gender, BMI, baseline CRP value (defined as the last CRP measurement prior to randomisation, or the first CRP following Dexamethasone for HCs), time from baseline, and whether they have a key comorbidity, defined as one or more of hypertension, diabetes or cardiovascular disease. An interaction between treatment and time from baseline will also be included in the model. CRP measurements more than 7 days after randomisation (or date of first CRP measurement following Dexamethasone initiation for HCs) will be removed from the analysis, so the comparison is over 7 days.

Due to the treatment by time interaction effect being included in the model, examining the treatment effect alone would be an inappropriate comparison, therefore the least squares means and 95% confidence intervals at the mean follow-up time will be compared between arms, which will take into account both the treatment effect and the treatment by time interaction. These means will be presented on the real scale, e.g. taking the antilog of the least squares mean if the dependent variable has been log-transformed. The difference between the least squares means (on the scale the model was fitted) and the standard error of the difference will be used to generate a treatment z-score, which will be compared against the normal distribution with mean 0 and variance 1, to obtain the two-sided p-value.

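### The interim re-estimation cannot secure the sample-size assumptions: its caps cover an SD only about 11–17% above plan, and the SAP's rule does not act on the SD

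*Protocol*

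**What the plan says.** The sample size is in Protocol 11.2.1, repeated in SAP 5. "Based on a mean of 99mg/L in the control group and a common standard deviation of 62mg/L derived from the literature", the protocol states that "a total sample size of 90 participants would provide sufficient power to detect a greater than a 40% relative difference for CRP", split as "30 participants in the active treatment group and at least 60 in the control", for 80% power at the 5% level.

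Protocol 5.1 places a re-estimation at 12 randomised participants and says: "This analysis will ensure that the assumptions made in the sample size calculation remain valid". If variability is higher than expected, up to 10 more participants may receive dornase alfa, for a total of 50. SAP 3 keeps both statements, moves the timing to 12 participants with Day 7 completed, and gives a total of 48.

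Protocol 6.5 accepts that other medicines given as best available care (BAC) may change CRP. It first refers this to the analysis plan, then adds that "a sample-size re-estimation is planned in order to take this potential source of unexpected variability into account".

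Protocol 11.4 makes the interim descriptive and gives no SD threshold or formula. SAP 12 instead computes conditional power from the observed standardised effect. Below 0.46 nothing changes, from 0.46 to 0.80 enrolment may rise, and above 0.80 nothing changes. The SAP maximum is 36 dornase alfa, 12 BAC and 72 historical controls.

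**The concern.** A reader of Protocol 5.1, Protocol 6.5 and SAP 3 would conclude that if CRP varies more than planned, the interim will detect it and the trial will be enlarged enough to keep its power. Three things must hold for that: the permitted increase must be large enough, the decision rule must respond to variability, and the interim data must measure the SD well enough. If they do not hold, the stated protection is not there, and a null result could be read as adequately powered because the documents say variability was dealt with.

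**Working it through.** **Inputs.** Control mean 99, SD 62, 40% difference, 30 v 60, 80% power, 5% level (Protocol 11.2.1). The calculation does not state sidedness; SAP 11.1 compares the z-score with the standard normal "to obtain the two-sided p-value", so two-sided is used. Caps are from Protocol 5.1 and SAP 12.

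**Step 1: reproduce N = 90.** Difference δ = 0.40 × 99 = 39.6 mg/L. The noncentrality is δ / (σ√(1/n₁ + 1/n₂)) = 39.6 / (62 × √(1/30 + 1/60)) = 39.6 / 13.86 = 2.86 on 88 df. Power is 80.7%. The next smaller 1:2 design, 29 v 58, gives 79.3%. The plan's figure reproduces, with little slack: 30 v 60 falls below 80% at an SD of about 62.5.

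**Step 2: how much SD the caps cover.** Solve the same power formula for the SD that gives exactly 80%.

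| Design | Source | Largest SD | Above 62 |
|---|---|---|---|
| 40 v 60 | Protocol cap, controls stay at 60 | 68.6 | 10.6% |
| 40 v 80 | Protocol cap, 1:2 kept | 72.4 | 16.8% |
| 36 v 72 | SAP cap, historical controls only | 68.6 | 10.7% |
| 36 v 84 | SAP cap, BAC arm pooled | 70.4 | 13.5% |

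As an illustration, at SD 77.5 (25% above plan) power is 61.8% at 30 v 60, 69.8% at 40 v 60 and 74.4% at 40 v 80. Reaching 80% would need 46 v 92.

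**Step 3: whether the SAP rule responds to the SD.** The SAP's interim set of about 30 out of 100 suggests an information fraction t = 0.3 (an assumption). Conditional power under the observed trend is Φ[(z₁/√t − 1.96) / √(1 − t)]. It equals 0.46 at z₁ = 1.03 and 0.80 at z₁ = 1.46. The mean of z₁ is √t × δ / (σ√(1/30 + 1/70)), because SAP 7 pools the BAC arm with the historical controls.

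- SD 62: mean 0.548 × 39.6/13.53 = 1.60. Below 0.46: Φ(1.03 − 1.60) = 28%. Promising zone: 16%.
- SD 80: mean 0.548 × 39.6/17.46 = 1.24. Below 0.46: Φ(1.03 − 1.24) = 42%. Promising zone: 17%.

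So higher variance hardly changes how often patients are added. It mainly moves trials into the lowest zone, where none are added. Simulating the rule with a full 1.2-fold increase whenever it is triggered, power at SD 80 goes from 62.1% to 63.5%, a gain of 1.4 points. These two figures start from 30 v 70 and use a normal approximation. They should not be compared directly with the 59% that the t-test gives for 30 v 60 at SD 80. Always enrolling to 36 v 84 would give 69.3% at SD 80, so the rule rarely uses even the increase it is allowed.

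**Step 4: precision of an interim SD.** The 95% interval is s√(df/χ²₀.₉₇₅) to s√(df/χ²₀.₀₂₅), with s = 62.

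- 12 patients in two arms, 10 df: 62√(10/20.48) to 62√(10/3.247) = 43 to 109.
- About 30 people, 28 df: 62√(28/44.46) to 62√(28/15.31) = 49 to 84.
- 60 historical controls, 59 df: about 53 to 76.

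Each upper limit lies above the 69 to 72 that the caps cover, and each lower limit lies well below 62.

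**The case against.** Several points on the other side stand and limit the conclusion.

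- The SAP decision does not rest on an SD from 12 patients. Its interim set is about 30 people, and all historical controls if there are too few to match. The interval of 43–109 applies to the protocol's description only.
- Protocol 6.5 puts the analysis plan first. The SAP follows through: analyses stratified by BAC treatment (8.3.1), a post-dexamethasone baseline for historical controls, a per-protocol exclusion for dornase alfa started before dexamethasone (6.2), and a second match on pre-dexamethasone CRP (11, 11.1). A reader might infer that the re-estimation is the only safeguard; the documents do not support that.
- A reader might infer that the trial will miss 80% power. That is not established. No document gives an SD of 75 or 80, and the 69–72 limit belongs to the unadjusted raw-CRP calculation. The primary model adjusts for baseline CRP and uses repeated measures, possibly on a log scale. If the baseline-to-follow-up correlation were 0.3, 0.5 or 0.6 (assumed; none is given), dividing by √(1 − ρ²) would raise the 40 v 80 limit from 72.4 to about 76, 84 or 91.
- The limits on enlargement are stated openly, and N = 90 is correct. There is no arithmetic error in the sample size.

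None of this supplies what the text promises. The SAP's rule still does not check the SD, and an adjusted model may widen the margin by an amount the documents do not give.

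**Conclusion.** The concern holds as a mismatch between a stated property and the design. Protocol 5.1 and SAP 3 promise that the interim keeps the sample-size assumptions valid and that extra variability brings extra patients. On the basis used for N = 90, the caps protect 80% power for a 40% difference only up to a raw-CRP SD of about 69 to 72 mg/L, 11–17% above plan. Under the SAP rule, with an information fraction of 0.3, patients are added about equally often at SD 62 and SD 80 (16% and 17%), and the gain at SD 80 is about 1.4 points. The interim SD is too imprecise to confirm or refute 62.

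The SD range assumes a two-sided unadjusted t-test on raw CRP. SD 80 is illustrative and not a forecast. The finding is that the assurance is unsupported, not that the trial is shown to be underpowered.

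**What to change.** 1. Reconcile Protocol 5.1, Protocol 6.5 and SAP 3 with SAP 12. Remove the assurance and the variability trigger, and describe the conditional-power rule as it is. Align the enrolment caps at the same time: Protocol 5.1 gives 50 and the SAP gives 48, while SAP 3 also allows 10 more on dornase alfa (40 + 10 = 50).
2. State the real limit with its basis: under the unadjusted calculation used for N = 90, the maximum increase preserves 80% power for a 40% difference only up to a raw-CRP SD of about 69–72 mg/L. Add that the adjusted, possibly log-scale repeated-measures model may tolerate a different SD.
3. At the interim, estimate the SD on the primary-analysis scale, pooled within group over all eligible historical controls and the randomised patients, with its confidence interval. If it exceeds the planning value, report the resulting detectable difference. The protocol says of the historical data: "A database of the first 120 participants with COVID-19 admitted to UCLH is available and being analysed currently".

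The cost is one calculation and changed wording in three places, with no extra patients. The stated protection becomes less favourable. The pooled SD will still be imprecise (60 controls alone give about 53–76), and historical controls may not reflect the care given during the trial, so they cannot by themselves show variability from drugs given to trial participants.
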